# Emergency Medicine Prospective Protocol

Caregivers that complete the TC check-in via photo submission or video chat will receive \$5 less in study incentives. The CPaSS tool will be used to collect data during the TC check-ins.

During the 6-month follow-up, we will also plan to administer a brief health literacy assessment, called the Newest Vital Sign. This valid and reliable tool will help us identify participants at risk for low health literacy in the study. This survey assessment will be self-administered and will last about 3 minutes.

## **5.1.4 End of Study Visit – (12 month follow-up visit)**

The last follow-up assessment will be administered at 12- months after the ED visit and will include both a self-administered computerized survey assessment (~15-20 minutes) and a TC check-in (a car seat check) administered by the RC (~10 minutes). The caregiver will have the option to complete the 12-month follow up survey in person at the visit or complete the survey on their own device (phone, iPad, laptop, etc.) prior to the follow-up visit. Allowing participants to complete the follow up assessment prior to the visit, will provide convenience to our participants and shorten the amount of time needed for the in person visit. Additionally, if participants move out of state, country or are unable to get to any of the study follow up site locations, then participants will have the option of completing the TC check-in (a car seat check) by submitting digital photographs to the study staff via text message or completing the check-in via video chat (e.g., Northwestern zoom, Microsoft teams, skype, duo, google hangout). Caregivers that complete the TC check-in via photo submission or video chat will receive \$5 less in study incentives. The CPaSS tool will be used to collect data during the TC check-ins.

### Follow-up protocol –retention of subjects

Retention will be maximized with established procedures from our prior work (80-90% compliance). The following protocol will be implemented to improve compliance with follow-up: 1) during the baseline assessment, the participant's name, address, e-mail account, phone number, Facebook and other social media accounts, and telephone numbers of two contact persons will be obtained; 2) reminder letters, telephone calls, text messaging, e-mail communication, and/or Facebook/other social media private messaging will be used for participants who agree to be contacted by such methods; 3) follow-up interviews will be scheduled at the participant's convenience including evenings and weekends; and 4) participants will receive an extra \$5.00 for confirming their follow up appointment or calling to reschedule it.

Additionally, we have set up two study e-mail accounts ([contact] and [contact]) to be used for subjects to contact study staff or for study staff to send appointment reminders to subjects. Through the study email account, we will also set up a Facebook and Instagram limited profile page. The Facebook and Instagram profile page lists only the study name and affiliation with LCH. Facebook or Instagram will NOT be used as a recruitment tool. The account is set up only as a source for private messaging between study staff and enrolled subjects who agree to be contacted via such methods. The message shows up in the person's private inbox, similar to an e-mail message. There is no ability to "friend" the study or post on the wall. Only subjects with active Facebook and Instagram accounts can be messaged. Privacy settings are checked on a monthly basis. When providing contact information, the subject will indicate if study staff can contact them through email, Facebook or Instagram.

## **5.2 Subject Withdrawal**

Participants (caregivers/parents) can stop taking part in this study at any time. Their decision will not affect their regular care or their child's care at LCH. If they wish to stop taking part in this

# Emergency Medicine Prospective Protocol

study, we ask that participants call the study team at [contact] or email us at [[contact]](mailto:[contact]). A study team member can speak to them about any concerns they may have. The study will then confirm their withdrawal from the study with a letter in the mail.

## 5.3 Early Termination Visits

Participants can stop taking part in this study at any time. Their decision will not affect their regular care or their child's care. If they wish to stop taking part in this study, we ask that participants call the study team at [contact] or email us at [[contact]](mailto:[contact]). A study team member can speak to them about any concerns they may have. The study will then confirm their withdrawal from the study with a letter in the mail.

## 6 Statistical Plan

### 6.1 Sample Size and Power Determination

Briefly, our calculations are based on two-sample comparisons between groups (e.g., control and TCBD) using results from our pilot study that assessed percent size-appropriate child passenger safety behaviors at 6-month follow-up (referred to as the “response rate” below). For analyses involving multiple time points, these calculations represent a conservative lower bound on the power that would only be achieved if the effective sample equals 1 observation per person (i.e. perfect within-individual correlation). For the calculations below we assume: a) 17% response rate among controls; b) 25% response rate among TCBD caregivers at 6 Month (with 75% of TCBD caregivers re-randomized); and c) only 80% of the target sample (n=204 controls and n=516 TCBD in the initial dichotomy) will be available for analysis at follow-up. Components (a) and (b) are based on pilot data where the control group received generic educational materials and outcomes were assessed at 6-months. Component (c) is a conservative correction for attrition. For Aim 2, we estimated power while accounting for uncertainty in the group sizes by simulating response and re-randomization patterns according to the above probabilities and testing for significant between-group differences; this process was repeated 10,000 times and the power was estimated as the percent of replications in which a between-group difference was identified. Binary Outcome: For the binary response case, if the observed response rate is at least 29.4% among those receiving enhanced TCBD, it can be reliably (>80% power) distinguished from a control response rate of 17%. Analogously, a response rate of at least 27.6% among basic intervention would be reliably (>80% power) distinguished from control. Converted to Cohen's  $h$ , both differences reflect small-to-medium effect sizes ( $h = 0.30$  and  $h = 0.26$ , respectively). Numeric Outcome (CPaSS): If the standardized mean difference (i.e. Cohen's  $D$ ) is  $>0.25$  (a small-to-medium effect size), we can reliably distinguish between control and basic TCBD conditions. Similarly, if  $D \geq 0.28$ , a small-to-medium effect size, we will have sufficient power (80%) to distinguish the control and enhanced TCBD conditions. Aim 2: Monte Carlo studies of linear latent trajectory models indicate that a medium level of heterogeneity among the slopes and/or intercepts of the trajectories can be reliably recovered (power  $> 80\%$ ) with a total sample size of  $n=200$ , with power exceeding 95% when the level of heterogeneity is high; given that our sample size soundly exceeds 200, we expect sufficient ability to determine the underlying characteristic trajectory types. Nevertheless, we further justify our sample size with a brief simulation study. Assuming a final sample size of 720, conservatively assuming individuals are only measured at an average of 25% of the 12 monthly assessments, we simulate data from a population with four equally likely trajectory types: consistently low, consistently high, linearly decreasing, and starting high then dropping off. Because we have no basis for estimating variability in the score, we assumed mean/variance equivalence, consistent with the Poisson distribution. Due to the time required to fit such models, we only completed 200 simulation replications, where we were able to correctly conclude (based on BIC) that there were four

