## ***3.2 Allocation to Interventional Group***

After completing the baseline survey, all caregivers will be randomized into one of two groups: 1) TCBD intervention group, or 2) control group. Computerized, block randomization (block sizes from four to eight) will be applied to assign eligible caregivers to the TCBD intervention or control group in a 3:1 ratio. Blocks will be stratified by age groups related to child passenger safety recommendations (<2 years – rear-facing CRS, 2-4 years – forward-facing CRS, 5-10 years – booster seat) and the child passenger safety behavior that led to eligibility for study (not using the recommended restraint currently or planning a premature transition in the coming 6 months).

After the 6-month follow-up assessment, caregivers in the intervention group only who continue suboptimal CRS use will be re-randomized by computer in a 1:1 ratio to receive either the basic or enhanced intervention. The enhanced TCBD will include one additional motivational interviewing (MI) session by phone in Month 7/8 and one to two additional tailored text messages in Months 7-12 (total of 7 tailored tips during these months compared to 4 tailored tips for those in the basic TCBD). The extra text messages will be sent to those in the enhanced TCBD group until size-appropriate restraint use is observed. Caregivers receiving enhanced TCBD will be encouraged to obtain a free seat check with a certified child passenger safety technician (CPST) in the community. The primary outcomes (size-appropriate CRS use and CPaSS) will be assessed in-person at Months 6 and 12. The secondary outcome, the CPaSS trajectory, is a measure of correct and consistent restraint use in response to the intervention and will be assessed by scoring photographs submitted by caregivers (Months 1-5; 7-11).

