### 4.2 Total Number of Subjects and Sites

To test the Tiny Cargo, Big Deal Intervention, we anticipate the need to screen 10,000 caregivers to recruit 900 caregivers who will be enrolled in the study and randomized to intervention or control. All recruitment will occur in the Emergency Department (ED) at Lurie Children's Hospital of Chicago (LCH) or remotely via phone/email/text message. With this most recent IRB modification (3/26/21), we will also add recruitment via flyers in patient treatment rooms from Lurie Children's affiliate EDs (e.g., Central DuPage, Northwest Community) and Lurie Children's Immediate Care Centers (Lincoln Park and Northbrook).

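### The power section assumes 204 controls and 516 TCBD, but 900 caregivers randomised 3:1 with 80% retention gives 180 and 540, and three of the four 80% power statements then fall 2 to 3 points short

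*Combined protocol and SAP*

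**What the plan says.** Section 4.2 plans to "recruit 900 caregivers who will be enrolled in the study and randomized to intervention or control". Section 3.2 says that computerised blocks will "assign eligible caregivers to the TCBD intervention or control group in a 3:1 ratio". After month 6, TCBD caregivers with continuing suboptimal restraint use are "re-randomized by computer in a 1:1 ratio to receive either the basic or enhanced intervention".

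Section 6.1 assumes a "17% response rate among controls", a "25% response rate among TCBD caregivers at 6 Month (with 75% of TCBD caregivers re-randomized", and that "only 80% of the target sample (n=204 controls and n=516 TCBD in the initial dichotomy) will be available for analysis at follow-up". The Aim 2 simulation in the same section starts from "Assuming a final sample size of 720", so 720 is the number analysed after attrition.

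On this basis section 6.1 makes four statements about 80% power:
- enhanced TCBD at 29.4% can be distinguished from control;
- for basic TCBD, "a response rate of at least 27.6% among basic intervention would be reliably (>80% power) distinguished from control";
- on CPaSS, a standardised difference of 0.25 separates basic TCBD from control;
- on CPaSS, 0.28 separates enhanced TCBD from control.

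Section 6.2 sets a two-sided 0.05 level for tests and power calculations.

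**The concern.** The total in section 6.1 agrees with the rest of the protocol and the split does not. Dividing by 0.80, 204 and 516 analysed correspond to 255 and 645 randomised. A 3:1 scheme for 900 gives 225 and 675. No other ratio and no differential attrition is mentioned anywhere.

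Under 3:1 the control group (180) is smaller than enhanced TCBD, basic TCBD or all TCBD, so it is the main limit on precision in each comparison with control. Overstating it makes the detectable effects look better than the randomisation scheme delivers. If instead 204/516 is what was intended, section 3.2 misdescribes the allocation, and that description has to match the programmed randomisation list.

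**Working it through.** **Inputs.** 900 randomised (4.2); TCBD:control 3:1 and re-randomisation 1:1 (3.2); 80% analysed, 75% of TCBD re-randomised, control rate 17%, and the four thresholds (6.1); two-sided 0.05 (6.2).

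**Group sizes.** Basic TCBD is taken as the month-6 responders plus half of those re-randomised: 0.25 + 0.75/2 = 0.625 of TCBD. Enhanced is 0.75/2 = 0.375 of TCBD.

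| | Randomised (control/TCBD) | Control analysed | TCBD analysed | Basic | Enhanced |
|---|---|---|---|---|---|
| As in 6.1 | 255/645 (2.53:1) | 204 | 516 | 322.5 | 193.5 |
| As in 3.2 | 225/675 (3:1) | 180 | 540 | 337.5 | 202.5 |

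Both rows total 720 = 0.80 × 900. The control groups differ by 204 − 180 = 24, and 24/180 = 13%.

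**Formulas** (Φ is the standard normal distribution function).
- Numeric: power = Φ(D/√(1/n₁ + 1/n₀) − 1.96); detectable D at 80% power = 2.8016 × √(1/n₁ + 1/n₀), where 2.8016 = 1.9600 + 0.8416.
- Binary (pooled z): power = Φ{[(p₁ − p₀) − 1.96√(p̄(1 − p̄)(1/n₁ + 1/n₀))] / √(p₁(1 − p₁)/n₁ + p₀(1 − p₀)/n₀)}.

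**Reproducing the plan, 204/516.**
- Basic: √(1/322.5 + 1/204) = 0.08946, so detectable D = 0.251, and power at 0.25 is Φ(2.795 − 1.96) = 79.8%.
- Enhanced: √(1/193.5 + 1/204) = 0.10035, so detectable D = 0.281, and power at 0.28 is Φ(2.790 − 1.96) = 79.7%.
- Basic 27.6% v 17%: p̄ = 0.2349; (0.106 − 1.96 × 0.03793)/0.03621 = 0.874; power 80.9%.
- Enhanced 29.4% v 17%: power 83.7%.
- Cohen's h is 0.296 and 0.256, matching the stated 0.30 and 0.26.

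To the whole percent these are 80, 80, 81 and 84, so the plan's statements reproduce, which also supports the definition of basic used here.

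**The same at 180/540.**
- Basic, D=0.25: √(1/337.5 + 1/180) = 0.09230; Φ(2.709 − 1.96) = 77.3%; detectable D = 0.259.
- Enhanced, D=0.28: √(1/202.5 + 1/180) = 0.10244; Φ(2.733 − 1.96) = 78.0%; detectable D = 0.287.
- Basic 27.6% v 17%: p̄ = (30.6 + 93.15)/517.5 = 0.2391; (0.106 − 1.96 × 0.03937)/0.03709 = 0.777; power 78.2%; detectable rate 27.9%.
- Enhanced 29.4% v 17%: power 81.9%; detectable rate 29.1%.

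| Comparison with control | Stated | At 204/516 | At 180/540 |
|---|---|---|---|
| Enhanced, 29.4% v 17% | above 80% | 83.7% | 81.9% |
| Basic, 27.6% v 17% | above 80% | 80.9% | 78.2% |
| Basic, D=0.25 | 80% | 79.8% | 77.3% |
| Enhanced, D=0.28 | 80% | 79.7% | 78.0% |

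**Dependence on the test, basic 27.6% at 180/540.** Arcsine 79.3%; exact chi-square about 78.5%; logistic Wald about 78.2% and likelihood ratio about 79.3%; unpooled z 81.5%. A continuity correction puts all four comparisons of this kind lower, but it also takes this one to 77.8% at the plan's own sizes.

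**Could 204/516 be the numbers before attrition?** No. They would total 720 rather than 900 randomised, and 163 controls and 413 TCBD analysed would give only about 70 to 75% power at the four thresholds.

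**All TCBD v control.** Section 6.1 gives no figure. The detectable effect at 180/540 is 27.1% v 17%, or D = 2.8016 × √(1/540 + 1/180) = 0.241. At 25% v 17%, power is 61% (pooled) to 63% (arcsine); at 204/516 it is 64 to 66%.

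**The case against.** The practical loss is small. Moving from 204/516 to 180/540 costs about 2 to 3 points of power, and the two CPaSS statements reach 80% at the plan's own sizes only by rounding. This stands, and it limits the weight of the point.

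The count of three depends on the test, which section 6.1 does not name. An unpooled z test leaves two shortfalls. This also stands, although the logistic model planned in section 6.2 puts the basic binary comparison just below 80%.

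The 29.4% for enhanced TCBD is not the pooled-z threshold at 204/516, which is 28.8%; the plan's exact method for that figure cannot be recovered. And the stated D values do not single out 204: control groups somewhat smaller or larger round to the same two decimals. They do rule out 180.

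The plan calls its assumptions conservative. At 3:1, 86% retention (774 analysed) would bring all four comparisons to 80% or more, and baseline adjustment could raise CPaSS power. But 80% is the retention the plan chose to state its power on, and it gives no baseline correlation. The lower-bound remark in section 6.1 concerns analyses of several time points, whereas section 6.2 frames Aim 1 at 12 months.

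Finally, 25% is a 6-month response rate used to set the re-randomised share; the plan does not offer it as the 12-month effect of all TCBD. The 61 to 63% is therefore context and not a failed statement, and the ratio conflict accounts for only 3 to 4 points of it.

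None of this reconciles the ratio with the group sizes.

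**Conclusion.** The concern holds. The 3:1 allocation, 900 randomised and 80% retention give 180 controls and 540 TCBD, not 204 and 516. That conflict is plain arithmetic and needs no assumption about the test.

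The effect on power is modest: 78.2%, 77.3% and 78.0% where 80% or more is stated, with only the enhanced binary comparison still above (81.9%). The clearest miss is basic TCBD on CPaSS. These figures rest on unadjusted two-sample calculations like the plan's own, exactly 75% of TCBD re-randomised 1:1, equal retention in both groups, and a pooled z test for the binary outcome; with an unpooled test, two of the four fall short.

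**What to change.** Check the programmed randomisation list and state one ratio throughout.

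- **If 3:1 is right:** in section 6.1 replace 204/516 with 180/540 and restate the effects detectable with 80% power as 27.9% and D=0.26 for basic TCBD and D=0.29 for enhanced. The 29.4% for enhanced can stay, since its power remains above 80%; the like-for-like threshold is 29.1%. Name the test used, and preferably rerun the original calculation with the corrected sizes so that all figures come from one method.
- **If 204/516 was intended:** correct section 3.2 to the ratio programmed, about 2.5:1, and leave the power figures.

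In either case it would help to add the detectable effect for all TCBD v control (27.1% v 17%, or D=0.24, at 180/540), since Aim 1 is framed as TCBD against usual care.

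The cost is wording only, with slightly less favourable figures. Keeping the present thresholds at 3:1 would instead mean enrolling more: D=0.25 is the binding one, and 720 × (0.2586/0.25)² ≈ 770 analysed, or 770/0.80 ≈ 963 randomised.

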
# Emergency Medicine Prospective Protocol

trajectory types in 100% of replications, and the mean trajectories in those four groups were characterized correctly.

**Exploratory Aim:** Aligning with the NIH guidance on health economics research, we plan a cost analysis of the intervention to inform wider dissemination and implementation in settings outside of the ED. Unmeasured time costs for staff or for participants can be a key barrier to the implementation and long-term viability of a new intervention since preventive and screening recommendations can compete for implementation time from staff. We will address this potential barrier by measuring all relevant costs associated with the study interventions through primary data collection. We will measure the total costs of the intervention from participant and health system perspectives by gathering estimates of intervention resource requirements, including personnel costs, implementation time, participant time, and material costs. Resource costs will include intervention development, training, and implementation. All costs will be adjusted to US 2017 dollars using the Gross Domestic Product Price Index. Control costs will be adjusted to reflect the proportion of time study participants spend on the app. We will calculate costs of the intervention per child. Net costs (savings) will be calculated by subtracting mean costs per participant in the control condition from mean costs per participant who receive the basic TCBD and the enhanced TCBD interventions. Given typical skewness, we will report means, medians, standard errors, minimum, maximum, and quantiles to provide information on cost measures. Tests will be employed to assess distributions of cost measures and identify appropriate methods for generating confidence intervals, such as non-parametric bootstrapping. We will also estimate cost-effectiveness as measured by dollars per caregiver using a size-appropriate CRS and using the CRS correctly. Economic data will provide key information about the relative costs and benefits associated with the intervention, inform scalability, and help prioritize future implementation strategies in EDs and other settings that serve young children (e.g., doctor's offices, schools).

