**Aim 2:** To use latent growth curve models to identify characteristic trajectories for the CPaSS observed in digital photographs over the 12 study months and assess for correlates of the trajectory types. We hypothesize that caregivers will have different CPaSS trajectories in response to the basic intervention, the enhanced intervention, and the control condition. We expect to identify at least four patterns of response. **Statistical Analysis:** We will determine 12-month CPaSS trajectory types using adaptations of finite mixture models for the case where the units are trajectories. We will define trajectory shapes through methods combining semiparametric regression modeling (e.g., generalized additive models), with latent class regression, using the R package flexmix. Following convention, we will use the Bayesian Information Criteria (BIC) to determine the appropriate number of latent classes, while also making practical considerations to avoid overfitting, such as not allowing overly small groups to be created, as in previous applied work. Using the posterior probability of class membership, we place individuals into trajectory groups and treat that grouping as the outcome in a subsequent multinomial regression model to determine correlates of class membership, including treatment group, caregiver race/ethnicity, and child age group. If substantial uncertainty in class membership is found, outcomes in the multinomial model will be weighted accordingly.

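### The 100% recovery of four trajectory classes holds only if caregivers within a class do not differ; with moderate differences, BIC in a model without a caregiver effect usually picks more than four

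*Combined protocol and SAP*

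**What the plan says.** Section 6.1 gives Aim 2 two supports: published Monte Carlo work on linear trajectory models at n=200, and the trial's own simulation. The simulation's inputs are:

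- Size: "Assuming a final sample size of 720". This is 204 controls + 516 TCBD, or 80% of 900.
- Data density: "individuals are only measured at an average of 25% of the 12 monthly assessments".
- True classes: "four equally likely trajectory types: consistently low, consistently high, linearly decreasing, and starting high then dropping off".
- Variability: "Because we have no basis for estimating variability in the score, we assumed mean/variance equivalence, consistent with the Poisson distribution".
- Replications: "we only completed 200 simulation replications", because of fitting time.

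The reported result is that BIC found four "trajectory types in 100% of replications, and the mean trajectories in those four groups were characterized correctly". Nothing in the description makes one caregiver score persistently above or below another in the same class.

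Section 6.2, Aim 2, plans flexible curves combined with latent class regression in flexmix. For the class count, "we will use the Bayesian Information Criteria (BIC) to determine the appropriate number of latent classes", with a further rule against very small groups that has no threshold. Class membership then becomes the outcome of a multinomial regression with treatment group among the predictors, weighted if membership proves uncertain. The section names no outcome distribution for the photograph score and no within-class caregiver effect. For Aim 1, the same section uses mixed models to represent correlation between repeated measurements on one person.

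**The concern.** Monthly photographs show the same child, seat and vehicle. Two caregivers who both belong to a consistently high class will usually still differ by a stable amount. A class model that treats the scores as independent given class can explain such stable differences only by splitting the class. With 720 caregivers, BIC has enough data to reward the split.

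The trajectory is the secondary outcome (sections 3.2 and 3.4.1), and class membership is the dependent variable in the model that relates trajectories to treatment. If the class count is inflated, some reported types would be slices of one type at slightly different levels. Because section 6.2 expects at least four patterns, extra classes would look like confirmation. The simulation cannot warn of this, since as described it contains no such variation.

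**Working it through.** **Inputs from section 6.1.** n = 720; each of 12 months observed with probability 0.25, so 0.25 × 12 = 3 scores per caregiver and about 720 × 3 = 2,160 in all; four classes at 25% each; variance equal to the mean. I read the description as independent scores given class.

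**Inputs assumed, because the documents give no CPaSS levels.** Setting A: low mean 4, high mean 16, drop-off between months 2 and 5. Setting B: low mean 10, high mean 40, drop-off between months 4 and 8. The fit is an EM algorithm for Poisson latent class regression with a cubic curve per class and six starts per class count. BIC uses n = observations unless stated.

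**Step 1: the plan's figure.** With no caregiver variation, four classes were chosen in 200/200 runs in A and in B, whether BIC counted persons or observations. The exact 95% lower limit for 200/200 is 0.025^(1/200) = 98.2%. The 100% therefore reproduces. It does depend on the unstated levels and shapes. In 100-run cells, still with no caregiver variation, recovery was 50% (4/16, mid-year drop), 94% (10/40, early drop), 53% (20/80, early drop) and 100% (20/80, mid-year drop).

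**Step 2: add within-class caregiver differences.** Each caregiver's mean is multiplied by a log-normal factor with coefficient of variation c. At mean m the between-caregiver variance is c²m² and the Poisson variance is m, so the within-class intraclass correlation is

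ICC = c²m² / (c²m² + m) = c²m / (1 + c²m).

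For c = 0.10 and m = 40 this is 0.4 / 1.4 = 0.29. For c = 0.15 and m = 16 it is 0.36 / 1.36 = 0.26. At the low means the same values of c give 0.09 (m = 10) and 0.08 (m = 4).

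Runs choosing four classes with no caregiver effect in the model, 50 per cell:

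| c | A | A, 5% minimum class | B | B, 5% minimum class |
|---|---|---|---|---|
| 0.05 | 50 | 50 | 49 | 50 |
| 0.10 | 49 | 50 | 0 | 1 |
| 0.15 | 13 | 17 | 0 | 0 |
| 0.20 | 1 | 5 | 0 | 2 |
| 0.30 | 0 | 7 | 0 | 0 |

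Without the minimum size, every failure in this table was an excess of classes: at c = 0.30, 6 to 8 in A and 8 (the largest tried) in B. The 5% threshold is also an assumption. A share from 50 runs carries at most about ±14 points (1.96 × √(0.25/50)).

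**Step 3: is this only a Poisson effect?** Total variance was held equal to the mean, as the plan assumes, with a share (the ICC) assigned to the caregiver. Gaussian class models with class-specific variances were fitted, 20 runs per cell. Four classes were chosen in:

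| ICC | means 10/30 | means 10/40 |
|---|---|---|
| 0 | 19 | 20 |
| 0.2 | 18 | 11 |
| 0.3 | 6 | 0 |
| 0.5 | 0 | 0 |

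Errors at ICC above 0 were all extra classes. With a 5% minimum, four were chosen in 8 and 2 of 20 at ICC 0.3, and in 0 and 2 of 20 at ICC 0.5. Dropping independence is enough to break recovery.

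**Step 4: put a caregiver effect in the class model.** With a gamma caregiver effect and 40 runs per cell, four classes were chosen in 40, 40, 39 and 26 runs in A, and 40, 40, 39 and 38 in B, at c = 0.10, 0.20, 0.30 and 0.50. In A the misses at 0.50 were too few classes (2 or 3). A separate check at means 10/30 and c = 0.20 chose 3 classes in 8 of 16 runs with a caregiver effect. The effect removes most of the excess but is not a complete cure.

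**The case against.** Several stronger readings are tempting, and the documents do not support them.

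- *The 100% is a wrong figure.* It is correct for the scenario simulated, as step 1 shows. The criticism is only that it does not transfer.
- *BIC will return too many classes.* This is conditional. At c = 0.05 four classes survive in 98% to 100% of runs, and in A they still do at c = 0.10. Other fits err the other way: at assumed means 5/15 with no caregiver variation, a Poisson fit chose 3 classes in 22 of 25 runs. A Gaussian fit with free class variances at c = 0.10 chose four in 15/20 (10/30), 12/20 (4/16, the rest 3) and 10/20 (10/40). By c = 0.20 that fit chose four in at most 1 of 20.
- *The planned analysis is a Poisson model that excludes a caregiver effect.* Poisson is stated for the simulation only. Aim 2 is labelled a latent growth curve analysis, which can carry random effects, and the reference list includes a paper on mixed models with mixture random effects. The gap is that section 6.2 does not state the structure.
- *The simulation has no improving class, so the pattern of interest was untested.* With every month equally likely to be observed and flexible curves, running time backwards turns the two falling shapes into rising ones with the same recovery. The fitted shapes are not restricted either.
- *The sample size rests on this simulation.* Section 6.1 sizes the trial on two-group comparisons, cites published work first for Aim 2, and offers the simulation as further support. No sample size changes.

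Two stated safeguards also count. The rule against very small groups helps, but its size is unstated and at 5% it repairs only part of the problem. Weighting for uncertain membership addresses the assignment of caregivers once the number of classes is fixed, not the number itself.

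**Conclusion.** The concern stands in a limited form. The simulation allows caregivers in one class to differ only by independent noise, and the planned latent class regression states no within-class caregiver effect. Once within-class differences reach a CV of about 0.10 to 0.20 (ICC roughly 0.2 to 0.3, depending on scale), BIC under conditional independence usually picks more than four classes. The 100% figure therefore says little about class recovery in the trial.

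This rests on assumed score levels, drop-off timing, cubic curves and a log-normal caregiver effect. The documents give neither the CPaSS scale nor any estimate of within-class variance, so the true value could lie below the threshold. The direction is consistent across fits at moderate to large variation; the exact threshold is not. Confidence is medium. Aim 1 is unaffected.

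**What to change.** In section 6.2, Aim 2: fit the class-specific curves with and without a within-class caregiver random intercept, using an outcome distribution checked against the data. Choose both the structure and the number of classes by BIC, and state the minimum class size.

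In section 6.1: say that the 100% figure holds only with no within-class caregiver variation, and report recovery from a re-run over a range of within-class variances. Improving classes and unequal class shares in that re-run are optional.

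The cost is SAP wording, slower fitting, one repeated simulation and probably a less favourable recovery figure. There is also some risk of too few classes when the random intercept absorbs level differences, which is why both structures should be fitted and compared. No trial procedure changes.
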